8.2.1. Inclusion Criteria

Two cohorts will be produced. First, a CPRD cohort, using linked primary care, medication, Hospital Episode Statistics, and socio-economic data, according to the following inclusion criteria:

- 1. Diagnosis of COPD before index date (time period will be defined in the SAP)
- 2. Aged ≥40 at index date.
- 3. Alive, and registered with a GP, at index date.
- 4. Not registered with a GP in the Greater Manchester area.

Second, a Salford cohort will be constructed using the Salford Integrated Record (SIR), according to the inclusion criteria:

- 1. Diagnosis of COPD before index date.
- 2. Aged ≥40 at index date.

WWEpi Project number: PRJ2282

3. Alive, and registered with a GP, at index date.

Restricted cohorts will then be constructed in both the Salford and CPRD populations, based on the inclusion/exclusion criteria and study period for the SLS:

- Patients with documented GP diagnosis of COPD, and currently receiving maintenance therapy
- 2. Male or female subjects aged ≥40 years of age at index date
- 3. Patients who have a history of treatment with systemic/oral corticosteroids, antibiotics (in association with GP contact) and/or hospitalisation for at least one COPD exacerbation in the 3 years prior to index date.
- 4. Current COPD Therapy

All patients currently receiving either:

- inhaled corticosteroid (ICS) alone or in combination with a long acting bronchodilator (this could be a fixed dose combination or an ICS/LABA provided in two separate inhalers, or ICS and LAMA),
- or long-acting bronchodilator therapy alone (e.g. tiotropium or salmeterol, or the use of two bronchodilators i.e. LABA/LAMA),
- or "triple therapy" i.e. ICS/LABA plus a Long Acting Muscarinic Antagonist (LAMA)

Finally, the third data source, the SLS, will be used as-is.

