6.1. Background

Chronic Obstructive Pulmonary Disease (COPD) is a chronic obstructive disease of the airways associated with a significant social and healthcare burden [1, 2, 3]. Most patients with COPD are managed in primary care, as reflected in recent UK guidelines, which are specifically targeted at primary care physicians [4]. The major goals of treatment are to relieve symptoms, improve activity/exercise tolerance, prevent and treat exacerbations, reduce mortality risk and improve health status. However, despite such guidelines, COPD remains under-diagnosed and under-treated; variations in treatments, standards of care and adherence to guidelines have been reported across different geographical regions [2, 5, 6, 7, 8].

Large computerised patient databases provide a useful source of real life observational data, and the General Practice Research Database (GPRD) has been successfully used to generate descriptive epidemiology data in COPD [9, 10, 11, 12] from a large group of UK primary care practices. Historically, the limitations of the GPRD were a time gap between data capture and availability for the researcher and limited links to other healthcare databases, although these are currently being addressed with the development of the Clinical Practice Research Datalink (CPRD) and in recent Phase 4 pragmatic clinical trials [12]. The use of electronic medical record (EMR) data in health research is a key objective in the Department of Health's national research strategy [13].

The Salford Lung Study (SLS) is an ongoing Ph IIIB pragmatic trial comparing a new once daily ICS/LABA fixed dose combination (RELVAR: fluticasone furorate + vilanterol) in which patients are identified by EMR, enrolled in their GP office, randomized to RELVAR or Standard of Care (SOC) maintenance therapy and followed for safety and effectiveness via linked primary care/secondary routine care with primary endpoint of COPD moderate/severe exacerbations over 12 months [14]. MHRA and NICE provided joint advice for the SLS protocol and were supportive of the design to generate "real world" evidence which will demonstrate the value and safety of the medicine against the most relevant standard of care.

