8.2.2. Exclusion Criteria

Subjects meeting any of the following criteria must not be included in the restricted cohorts:

- 1. Patients with any life threatening condition or uncontrolled/clinically significant disease (code list to be specified in the Study Analysis Plan)
- Patients with unstable COPD: Patients with an exacerbation (defined by treatment with oral corticosteroids and/or antibiotic or hospital discharge listing COPD) with an onset within 2 weeks of index date. Delay index date until at least 2 weeks after the onset of an exacerbation and until the exacerbation has resolved.
- Chronic user of oral corticosteroids: Subjects who are considered to be a chronic user of oral corticosteroids for respiratory or other indications (Algorithm to be specified in the Study Analysis Plan).
- 4. In the Salford population only, those patients who are entered in the SLS and randomised to the RELVAR arm.

WWEpi Project number: PRJ2282

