10. MANAGEMENT AND REPORTING OF ADVERSE EVENTS/ADVERSE REACTIONS

This is a retrospective study. From the CPRD, free text data will not be available to allow causality determination of any potential adverse events. Adverse events arising from the SLS trial will have previously been reported appropriately during the trial period.

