Annex 2: Code lists for key definitions using in study PRJ2282/201491

- 1. Medical codes considered to identify those with COPD in the CPRD
- 2. Code lists for moderate/severe COPD exacerbation used in CPRD and SLS-EHR
- 3. Code list to define Hospitalised pneumonia (PO3 and SO2) in CPRD

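### Eligibility is read from records in CPRD but accepted from trial enrolment in SLS, so a selection artefact of unknown sign could pass as a Hawthorne effect in PO2

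*Protocol*

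**What the plan says.** Section 8.2.1 sets out how the comparison groups are formed: "Restricted cohorts will then be constructed in both the Salford and CPRD populations, based on the inclusion/exclusion criteria and study period for the SLS". One criterion is a history of treatment "and/or hospitalisation for at least one COPD exacerbation in the 3 years prior to index date". Section 8.2.2 adds exclusions for the restricted cohorts, to be put into operation by a code list and an algorithm, for example: "Subjects who are considered to be a chronic user of oral corticosteroids for respiratory or other indications (Algorithm to be specified in the Study Analysis". Section 8.2.1 then closes with "Finally, the third data source, the SLS, will be used as-is".

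Section 8.1 makes the main contrast the whole enrolled SLS SOC arm against CPRD patients who would have qualified. On entry to the trial, section 6.1 says "patients are identified by EMR, enrolled in their GP office". On the CPRD side, section 10 notes "From the CPRD, free text data will not be available".

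For PO2, section 8.7.1 pools SLS and CPRD in a multilevel model with SLS as one distinct region, enters all listed confounders, and applies backward selection by AIC. An SLS random effect outside the 2.5-97.5 percentile range of the regional effects is then taken as evidence of a Hawthorne effect. PO3 and SO1 follow the same approach.

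**The concern.** A CPRD patient is in the comparison only if the records show a qualifying exacerbation and trip none of the coded exclusions. An SLS patient is in because the trial enrolled them, and no re-screening by the same program is stated. A participant whose record shows no qualifying event, or who would fail a coded exclusion, stays in; a CPRD patient with an identical record is left out.

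This matters most for PO2. The entry criterion and the outcome both rest on steroid or antibiotic treatment, GP contact and hospital admission (sections 8.2.1 and 8.3.1; the exacerbation code-list section of Annex 2). Selecting one side on recorded past events therefore bears on recorded future events. Because the percentile rule is two-sided, an artefact in either direction could place SLS outside the range and be read as changed behaviour.

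**Working it through.** The protocol gives no exacerbation rate, no effect of prior exacerbation on outcome and no share of SLS patients lacking a coded event. There is no planned figure to reproduce. The check has two parts.

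**1. Does any planned safeguard close the gap?**

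- *Previous exacerbation as a covariate (8.3.3).* It enters the model, but backward AIC (8.7.1) does not guarantee that it stays. If it is defined over 3 years, SLS patients with no coded event have no counterpart in the eligible CPRD cohort, and adjustment there is extrapolation. With a shorter look-back, CPRD patients whose event was less recent would share that category with SLS patients who have no coded event at all. The definition is left to the SAP.
- *Eligible Salford records against SLS (8.7.1).* Descriptive, and under PO1; it does not enter the PO2 model.
- *Rates in the 12 months before index (8.3.1).* Conditional on technical feasibility, and 12 months does not test a 3-year criterion.
- *SO3.* A before-and-after comparison that supports PO2 but does not align eligibility between SLS and CPRD.
- *CPRD within Greater Manchester (8.9).* That eligible cohort is also selected from records, so the asymmetry remains.

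**2. What size and direction are possible?** Every input here is an assumption.

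Let q and p be the shares of SLS and CPRD patients with a true prior exacerbation, and RR the outcome rate ratio, prior against none. With no true difference between settings, the crude ratio is

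SLS/CPRD = [q + (1 - q)/RR] / [p + (1 - p)/RR].

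| q | p | RR 1.5 | RR 2 | RR 3 |
|---|---|---|---|---|
| 1.00 | 0.63 | 1.141 | 1.227 | 1.327 |
| 1.00 | 0.86 | 1.049 | 1.075 | 1.103 |
| 1.00 | 0.95 | 1.017 | 1.026 | 1.034 |
| 0.95 | 0.95 | 1.000 | 1.000 | 1.000 |
| 0.90 | 0.95 | 0.983 | 0.974 | 0.966 |

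Worked entry: q = 1.00, p = 0.86, RR = 2 gives 1/(0.86 + 0.14/2) = 1/0.93 = 1.075.

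The values 0.63 and 0.86 borrow the positive predictive values quoted in the Annex 2 code-list section. They are a pessimistic choice: they belong to the outcome algorithm and are treated here as per-event values. With two independent coded events, the chance that at least one is true is 1 - (1 - 0.63)² = 0.863 or 1 - (1 - 0.86)² = 0.980; with three, 0.949 or 0.997.

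The opposite case: suppose a share u of SLS patients has no coded event and 0.4 times the event rate of the rest, while every CPRD patient has one. The ratio is (1 - u) + 0.4u = 1 - 0.6u, that is 0.97, 0.94 and 0.85 at u = 5%, 10% and 25%.

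The apparent ratio therefore falls on either side of 1 depending on ascertainment that the documents do not describe. It is also a crude ratio. The planned conclusion depends on where the adjusted SLS random effect lies among the regional effects, whose spread is not given, so these figures cannot be turned into a probability of a false Hawthorne finding.

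**The case against.** The best reply is that both sides are enriched. The criteria applied to CPRD are those of the trial, and section 6.1 says that SLS patients were also found through electronic records. This stands. A reader might infer that CPRD is enriched and SLS is not; the documents do not support that. They show a difference in ascertainment and only a possible difference in enrichment.

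A reader might also infer that the bias lowers SLS relative to CPRD and so mimics a Hawthorne benefit. That does not follow: the coded exclusions and misclassified history in CPRD can act the other way. Nor do the documents rank prior exacerbation as the strongest predictor. For PO3 in particular, history of pneumonia is a separate listed covariate and no link from prior exacerbation to pneumonia is quantified.

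Two further points stand. PO2 is about the SOC arm of the trial and section 8.1 specifies all enrolled SOC patients, so making a re-screened subset primary would change the question. And the exclusion codes are properly deferred to the SAP. Sections 8.7.3 and 8.9 also admit that definitions and data collection may differ between the sources.

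None of this answers the remaining point: the protocol itself settles that SLS is taken as enrolled, and it states no analysis that puts both sides through the same eligibility program.

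**Conclusion.** The point holds as one of unequal ascertainment. The same nominal criteria are applied through retrospective records in CPRD and through trial enrolment in SLS. For PO2 the prior-exacerbation criterion comes from the same kinds of record as the outcome, so a selection artefact could be read as a Hawthorne effect under the percentile rule. The listed safeguards narrow this but leave it open.

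Its sign and size are unknown. The illustrative range of 0.85 to 1.33 rests wholly on assumed values and a crude ratio; it shows that either direction is possible and estimates nothing. The concern is weaker for PO3, where the outcome is hospitalised pneumonia. It is not a reason to abandon the as-is SOC arm as the main comparison.

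**What to change.** Keep the as-is SLS SOC arm as the primary set and add to the protocol or SAP:

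1. For PO2, and for PO3 and SO1 where data allow, a prespecified sensitivity analysis that runs the CPRD eligibility program (restricted-cohort criteria and coded exclusions) on the pre-index records of SLS SOC participants at their entry date and restricts to those who pass.
2. A table of the share of SLS SOC participants failing each rule.
3. A statement that the Hawthorne conclusion will be interpreted in light of both results. If only the as-is analysis places SLS outside the range, selection should be named as a possible explanation.
4. Previous exacerbation retained in the PO2 and PO3 models regardless of AIC.

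The cost is modest. Annex 2 already lists "Code lists for moderate/severe COPD exacerbation used in CPRD and SLS-EHR", and coded criteria are to be run on Salford records in any case. The sensitivity analysis will have fewer SLS patients. Two things need confirming first: that the SLS records reach back 3 years before entry, which the conditional wording on the prior 12 months leaves open, and that the coded exclusions as well as the exacerbation codes can be run on them.

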8.2.2. Exclusion Criteria

Subjects meeting any of the following criteria must not be included in the restricted cohorts:

- 1. Patients with any life threatening condition or uncontrolled/clinically significant disease (code list to be specified in the Study Analysis Plan)
- Patients with unstable COPD: Patients with an exacerbation (defined by treatment with oral corticosteroids and/or antibiotic or hospital discharge listing COPD) with an onset within 2 weeks of index date. Delay index date until at least 2 weeks after the onset of an exacerbation and until the exacerbation has resolved.
- Chronic user of oral corticosteroids: Subjects who are considered to be a chronic user of oral corticosteroids for respiratory or other indications (Algorithm to be specified in the Study Analysis Plan).
- 4. In the Salford population only, those patients who are entered in the SLS and randomised to the RELVAR arm.

WWEpi Project number: PRJ2282

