8.2. Setting

In terms of geography, Salford, UK, and surrounding areas within Greater Manchester, for the SLS group; UK-wide, excluding Greater Manchester, for the CPRD group. In terms of health settings, general practice – restricted to practices in Salford and to practices that contribute to CPRD (~10%).

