8.4. Data sources

The three main data sources are SLS, CPRD and SIR.

The Salford Lung Study (SLS) is described in [14]. In brief, it is a pragmatic trial, carried out in Salford, UK, to evaluate the relative effectiveness and safety of RELVAR compared with SOC. There are two separate studies within the SLS; one for COPD and the other for asthma. For this protocol, the SLS data refers to SLS for COPD only.

WWEpi Project number: PRJ2282

The CPRD is a primary care database consisting of a subset of GP practices across the UK. This will be linked to Hospital Episode Statistics (HES), socio-economic status (SES) and Office of National Statistics (ONS) datasets. For brevity, the linked dataset will henceforth be referred to as CPRD.

The SIR is a comprehensive primary and secondary care database detailing healthcare contacts, diagnostic tests and prescriptions of all patients registered with a GP in Salford, UK.

There are a range of subsets and derivations of the data sources that will be considered for this study, listed here for clarity.

CPRD: CPRD – all practices, all COPD patients

CPRD-GM: CPRD – practices/patients in Greater Manchester only, all COPD patients

CPRD-xGM: CPRD – excluding practices/patients in Greater Manchester, all COPD patients

CPRD-GM-IC: CPRD – practices/patients in Greater Manchester only, COPD patients meeting SLS inclusion criteria only

CPRD-xGM-IC: CPRD – excluding practices/patients in Greater Manchester, COPD patients meeting SLS inclusion criteria only

SLS-E: SLS – all eligible. Not all of these are enrolled (some decline)

SLS: SLS - all enrolled

SLS-SOC: SLS – SOC arm only

SIR: SIR – all COPD patients

SIR-IC: SIR - COPD patients meeting SLS inclusion criteria only

In the CPRD, data linkage will be subject to a lag due to the delayed availability of HES and ONS data. Fully linked data will only be available up to a certain date when analyses are undertaken, and as such, primary analyses will be restricted to include SLS enrolled patients up to that date. Subsequent analyses will be conducted once linkage is available for the entire recruitment period. As capture of events of serious pneumonia (as defined in the context of this study) is dependent on records of hospitalisation, PO3 will be analysed when fully linked CPRD-HES data are available.

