8.7. Data analysis

8.7.1. Essential analysis

All analyses will be conducted using SAS.

For PO1, distributions of the confounders and effect modifiers (as listed in Section 8.3.3) will be tabulated – summarised as proportions in each category for binary and categorical variables, and means/medians and standard deviations for continuous variables. Graphical visualisations will also be produced to aid interpretation (for example, boxplots to characterise age distributions in each population, stacked bar charts to visualise SES by population). This will be done for a series of the derived populations to separate out true differences in demographics in Salford and differences that arise as a consequence of data quality issues etc. The following comparisons will be of interest:

- CPRD-GM v CPRD-xGM: to give an indication of true demographic difference from the same data source.
- CPRD-GM-IC v CPRD-xGM-IC: as above, but restricted to patients meeting the inclusion criteria.
- SIR v CPRD-GM: to give an indication of differences arising as a consequence of selection bias of CPRD practices, and through data quality issues etc.
- SIR-IC v CPRD-GM-IC: as above, but restricted to patients meeting the inclusion criteria.
- SIR-IC v SLS-E: to give an indication of recruitment bias and physician researcher bias (at the approach stage).
- SIR-IC v SLS: to give an indication of recruitment bias (at recruitment stage).
- SLS v CPRD-xGM-IC: to indicate the difference between trial recruited, and those
 meeting the inclusion criteria outside of Salford. This is the key comparison for
 addressing PO1.

WWEpi Project number: PRJ2282

We will then move on to explicit modelling of regional variation of the characteristics within CPRD for the emboldened comparison (SLS v CPRD-xGM-IC) to ascertain whether the characteristics observed within Salford are unusual by comparison with CPRD-xGM-IC. We will take local authority regional level (anonymised) as the comparable unit to the study region for SLS. SLS will be considered unusual on a given demographic if an appropriately chosen summary statistic for that demographic (mean for continuous variables) falls outside the 2.5-97.5 percentile range.

For PO2, we will commence with exploratory analyses, similar to described above, to explore the distributions of the primary and secondary endpoints.

Hawthorne effect will be evaluated in two different ways.

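### Exclusion item 4 takes the RELVAR arm out of the Salford eligible pool (SIR-IC) but not out of the SLS sets compared with it, so the two recruitment-bias comparisons are distorted

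*Protocol*

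**What the plan says.** **How the Salford pool is built.** Protocol 8.2.1 states: "Restricted cohorts will then be constructed in both the Salford and CPRD populations, based on the inclusion/exclusion criteria and study period for the SLS". The Salford cohort comes from the Salford Integrated Record (SIR). Section 8.2.2 opens its list with "Subjects meeting any of the following criteria must not be included in the restricted cohorts", and item 4 of that list reads "In the Salford population only, those patients who are entered in the SLS and randomised to the RELVAR arm". Section 8.4 labels the resulting set "SIR-IC: SIR - COPD patients meeting SLS inclusion criteria only".

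**What it is compared with.** Section 8.4 defines "SLS: SLS - all enrolled", and defines SLS-E as all eligible patients, including those who declined. Section 8.2.1 says the SLS data are taken without further selection. A SOC-only set, SLS-SOC, is also defined in 8.4, but the comparisons discussed here do not use it.

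**The comparisons.** Section 8.7.1 lists SIR-IC v SLS-E as an indication of bias at the approach stage. The next item is "SIR-IC v SLS: to give an indication of recruitment bias (at recruitment stage"). Nothing in the protocol lifts item 4 for either one.

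**Area.** Section 8.2 gives the setting as "Salford, UK, and surrounding areas within Greater Manchester, for the SLS group", but its following sentence limits the practices to Salford. SIR holds the contacts, tests and "prescriptions of all patients registered with a GP in Salford, UK" (8.4).

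**The concern.** Recruitment bias is the difference between the patients recruited and the eligible pool they came from. Item 4 removes part of the recruits from the pool and leaves them among the recruits. The pool then over-represents patients who did not enrol, and the recruits look less typical of it than they are.

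Excluding RELVAR-arm patients is understandable where outcomes under standard care are compared. These PO1 comparisons tabulate patient characteristics, so the treatment received gives no reason to drop anyone.

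The two comparisons are the steps in 8.7.1 meant to show where selection entered, at the approach to patients or at their recruitment. If the pool is altered, the recruitment effect is overstated and part of it can appear at the wrong stage.

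**Working it through.** The protocol gives no figure to reproduce here. It states no number eligible, no enrolled share and no allocation ratio. The check follows from the definitions.

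**Inputs**
- Enrolled target: 2,800 (Protocol 8.5).
- r, the share of enrolled patients randomised to RELVAR: 0.5, assumed. Item 4 then removes about 1,400 patients.
- p, the share of eligible Salford patients who enrolled: assumed, varied from 0.10 to 0.80.
- E and N, the mean or proportion of a characteristic in enrolled and non-enrolled eligible patients, with d = E - N.
- All enrolled patients are taken to be in the Salford pool. By randomisation, each arm has expected value E.

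**Step 1. Full pool.** Its value is pE + (1 - p)N, so SLS minus pool = (1 - p)d.

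**Step 2. Pool after item 4.** SIR-IC = [(1 - r)pE + (1 - p)N] / (1 - rp), so SLS minus SIR-IC = (1 - p)d / (1 - rp). Compared with step 1, the gap is multiplied by 1/(1 - rp), which is 1/(1 - p/2) when r = 0.5.

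**Step 3. SIR-IC v SLS-E.** Suppose SLS-E is exactly the eligible pool, so there is no approach-stage bias. The true gap is 0. The gap shown is (1 - p)d × rp/(1 - rp).

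| p | Eligible pool (2,800/p) | SIR-IC after item 4 | Factor on SLS v SIR-IC | Spurious SLS-E v SIR-IC gap, share of d |
|---|---|---|---|---|
| 0.10 | 28,000 | 26,600 | 1.05 | 5% |
| 0.20 | 14,000 | 12,600 | 1.11 | 9% |
| 0.25 | 11,200 | 9,800 | 1.14 | 11% |
| 0.40 | 7,000 | 5,600 | 1.25 | 15% |
| 0.50 | 5,600 | 4,200 | 1.33 | 17% |
| 0.80 | 3,500 | 2,100 | 1.67 | 13% |

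**Example (assumed values).** Take E = 50%, N = 40% and p = 0.5. The full pool is 0.5 × 50 + 0.5 × 40 = 45.0%, so the SLS gap is 5.0 points. After item 4, SIR-IC is (0.25 × 50 + 0.5 × 40)/0.75 = 43.3%. The SLS gap becomes 6.7 points, and SLS-E shows a gap of 1.7 points where the true one is 0. With both arms kept in SIR-IC, the factor is 1.00 and the SLS-E artefact is 0.

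**Area.** If a share g of SLS participants were registered outside Salford and a characteristic differed by 10 points between the areas, the SIR comparisons would carry a further gap of g × 10 points, for example 1 to 3 points for g = 0.1 to 0.3. Both values are assumed. The protocol does not say whether g is above zero.

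**The case against.** **The effect is only a reweighting, in minor comparisons.** This is true and limits the point. Because the removed patients are a random part of the enrolled, SLS v SIR-IC scales a gap that already exists and, in expectation, neither creates nor reverses one. The two comparisons are descriptive, with no test or threshold. The percentile rule in 8.7.1 is attached to SLS v CPRD-xGM-IC, which does not use SIR-IC. The SLS-E comparison is more exposed: whenever enrolled and non-enrolled patients differ, it can show a gap where approach-stage bias is nil.

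**The label in 8.4 mentions inclusion criteria only, so item 4 may not have been meant to apply.** That is possible. But 8.2.2 expressly bars these patients from the restricted cohorts, and an analyst following it would drop them. If the other reading is intended, the protocol should say so.

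**PO1 is worded for the SOC arm, so the all-arms SLS set may be the item to correct.** The two wordings do differ. Substituting SLS-SOC would not cure the distortion, however. The SOC arm also has expected value E, so the gap to the reduced pool is still (1 - p)d/(1 - rp).

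**Stronger readings that the documents do not support.**
- A reader might count it as a fault that SOC patients are on both sides. Any contrast of recruits with the pool they came from has that overlap. The fault is the one-sided removal of an arm.
- A reader might infer that enrolled v not enrolled is the right replacement. That contrast equals d, which is the recruits-v-pool gap multiplied by 1/(1 - p): 1.25 at p = 0.2 and 2.00 at p = 0.5. It answers a different question.
- A reader might take it as settled that SLS reaches beyond SIR's area. That rests on one phrase in 8.2. The next sentence there, the abstract and the trial description in 8.4 all point to Salford.

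**Conclusion.** The point holds for the two recruitment-bias comparisons. As written, item 4 takes one randomised arm out of SIR-IC while SLS and SLS-E keep it. With 1:1 allocation assumed, the SLS v SIR-IC gap is overstated by 11% at p = 0.2 and 33% at p = 0.5. If SLS-E equals the eligible pool, about 11% (p = 0.25) to 17% (p = 0.5) of any enrolled/non-enrolled difference appears as approach-stage bias that does not exist. The actual size cannot be fixed, because the protocol states neither p nor the allocation ratio.

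The area question is a separate inconsistency within 8.2. It affects these comparisons only if some SLS participants are registered outside Salford.

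A reader might conclude that the study's main answers are at risk. They are not: the key PO1 comparison, PO2 and PO3 are untouched by this point. It is worth correcting because these supporting comparisons would otherwise not measure what 8.7.1 says they measure.

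**What to change.** 1. In 8.2.2, state that item 4 applies to outcome analyses only, and that SIR-IC keeps both SLS arms in the comparisons with SLS-E and SLS. Align the SIR-IC label in 8.4 with this.
2. If enrolled v not enrolled is also of interest, it can be added from the third grouping in 8.3.2 (Salford COPD patients outside SLS), limited to those meeting the SLS criteria. Label it as a different contrast from recruits v pool.
3. Reconcile the two descriptions of the SLS area in 8.2. If any participants are registered outside Salford, restrict SLS and SLS-E to Salford-registered patients in the SIR comparisons only.

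The cost is a sentence or two and, if needed, a filter on practice. Applying item 4 already requires SLS patients and their arm to be identified within SIR, so no new linkage is needed. Any participants outside Salford would leave the SIR comparisons and stay in all others.
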